**Identify exclusion criteria.**

**Title :** An RCT of a Primary Care-Based PTSD Intervention: Clinician-Supported PTSD Coach  
**Approval Period:** Draft

Patients will be excluded if they demonstrate symptoms that would not allow them to engage in the CS PTSD Coach (i.e., 1) gross cognitive impairment, 2) current symptoms of mania or psychosis) or who have more pressing concerns needing attention first (i.e., 3) suicide attempt in the last 2 months or current suicidal intent). We will also exclude patients who 4) are already receiving psychotherapy or MH counseling, 5) started or changed psychotropic medication for PTSD in the last 2 months prescribed outside of VA PC, and 6) prefer to be directly referred to MH specialty care.

- i) Describe your screening procedures, including how qualifying laboratory values will be obtained. If you are collecting personal health information prior to enrollment (e.g., telephone screening), please request a waiver of authorization for recruitment (in section 15).**

We will use chart review to identify potential participants. A list of patients who have screened positive for PTSD (using the PC-PTSD screen) in primary care will be generated. A waiver of authorization for recruitment will be obtained for this approach.

During the phone screen (see attachment), potential participants will be informed about whom the study wishes to recruit, including a description of common PTSD symptoms. Potential participants will be asked if they believe they would be appropriate for the study based on whether or not they have those types of symptoms. For those who are not sure, the 4 item PC-PTSD screen will be administered.

- j) Describe how you will be cognizant of other protocols in which participants might be enrolled. Please explain if participants will be enrolled in more than one study.**

We will ask potential participants if they are enrolled in any other research studies that would conflict with their participation in this one. Participants may be enrolled in studies unrelated to this one.

- k) Payment/reimbursement. Explain the amount and schedule of payment or reimbursement, if any, that will be paid for participation in the study. Substantiate that proposed payments are reasonable and commensurate with the expected contributions of participants and that they do not constitute undue pressure on participants to volunteer for the research study. Include provisions for prorating payment. See payment considerations**

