## Design and Methods Overview

This study is a two-site, two-arm, parallel RCT. Veterans with PTSD ( $N = 260$ ) will be recruited from VA PC clinics at Syracuse and Palo Alto. Participants will be randomized in equal proportions to receive 1) PC-MHI treatment as usual (PC-MHI TAU) or 2) CS PTSD Coach. Assessments will occur at baseline, 8 (post-treatment), 16, and 24 weeks post-baseline. Primary outcomes will be changes in PTSD severity and engagement in 2 sessions of specialty MH treatment. Thirty CS PTSD Coach participants will also complete a brief qualitative interview at post-treatment to evaluate their satisfaction with care. The study will use cutting-edge methodologies, including an innovative intervention package and objective app usage data to overcome limitations of self-report data.

**Data Collection Methodology.** The table below presents the measures that will be employed at each assessment time point. Baseline assessments will be conducted in person. Research staff will obtain informed consent and HIPAA authorization. Next self-report measures will be administered to assess inclusion criteria. Within one week of baseline (and prior to session 1 of CS PTSD Coach) participants will complete the CAPS-5 by phone with an independent assessor blind to condition. A post-treatment assessment (8 weeks) and two follow-up assessments (16 weeks and 24 weeks) will be conducted following baseline (Table 3). Follow-up assessments will be in person or by phone (based on participant preference) by local study staff, with the exception of the post-treatment CAPS-5, which will be conducted by phone by the independent assessor blind to condition. Several aspects of our assessment procedures, including options to assess by phone and brief assessment batteries, were designed to reduce participant burden and minimize drop-out.

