**Table of Measures**

Measure	Construct	0 wk	8 wk	16 wk	24 wk
Blessed Orientation Memory Concentration	Cognitive Impairment	X			
Demographics & Military Background	Demo & Military Service	X			
Columbia-SSRS	Suicidal Ideation	X	X	X	X
Alcohol Use Identification Test (AUDIT)	Alcohol Use	X	X	X	X
Drug Abuse Screening Test (DAST)	Drug Abuse	X	X	X	X
Clinician Administered PTSD Scale-5 (CAPS-5)	PTSD (interview)	X	X		
VA Administrative Data	Treatment Engagement	X			X
Client Satisfaction Questionnaire (CSQ)	Treatment Satisfaction		X		
Patient Feedback Interviews	Patient Feedback		X		
Coping Self-Efficacy Scale	Coping Self-Efficacy	X	X	X	X
Patient Health Questionnaire-9 (PHQ-9)	Depression	X	X	X	X
WHO QOL-BREF	Quality of Life	X	X	X	X
PTSD Checklist-Specific-5 (PCL-5)	PTSD (self-report)	X	X	X	X

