The objective of Aim 2 is to correlate treatment arm with engagement in specialty MH care. We will evaluate the effect of the CS PTSD Coach condition on rate of attendance to at least 2 specialty MH visits post randomization (week 1 to week 24). To evaluate whether rates of attendance differ by condition, we will fit a mixed effects logistic regression model with a subject-specific random effect, an indicator for condition, and indicators for each time point. We are particularly interested in the effect of condition at 24 weeks. The parameter of interest, therefore, is the interaction term that corresponds to rate of treatment attendance at 24 weeks.

Several approaches will be used to evaluate our Exploratory Aims. To explore potential mediators (i.e., amount of app use, improvement in coping self-efficacy), we will fit 2 models for each potential mediator. One will include condition only and the second will include condition and the potential mediator. Change in the coefficient corresponding to condition after inclusion of the mediator may indicate a mechanism of action. To examine possible moderators (e.g., baseline PTSD severity), interaction terms between possible moderators and condition will be assessed. Significant interaction terms will suggest that the effect of intervention varies by

levels of the moderator. Lastly, to evaluate symptom trajectories over time, we will consider a mixed effects model of PCL scores at all time points with indicators for each follow-up visit (at 8, 16, and 24 weeks), randomization group, and an interaction between the indicators for time and condition as represented by the 3 product terms. A test evaluating all 3 product terms will address whether CS PTSD Coach affects the overall trajectory of PCL score. We will also explore if trajectories are moderated by continued PTSD Coach use and receipt of MH treatment. A similar approach proposed to test Aim 1 will be used to determine if CS PTSD Coach has broader effects, beyond PTSD symptom improvement, on depression and quality of life.

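### Aim 2 (a primary outcome): one yes/no per person over 24 weeks, but the named test is an interaction in a repeated-measures logistic model that does not list it

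*SAP*

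**What the plan says.** The SAP's Design and Methods Overview makes engagement a primary outcome: "Primary outcomes will be changes in PTSD severity and engagement in 2 sessions of specialty MH treatment".

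The Aim 2 paragraph under Data Analysis and Statistical Considerations then makes four statements:

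- Outcome: "rate of attendance to at least 2 specialty MH visits post randomization (week 1 to week 24", which is one binary result per participant.
- Model: mixed effects logistic regression with "a subject-specific random effect, an indicator for condition, and indicators for each time point".
- Target: "We are particularly interested in the effect of condition at 24 weeks".
- Test: "The parameter of interest, therefore, is the interaction term that corresponds to rate of treatment attendance at 24 weeks".

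Three other places bear on how the data would be laid out:

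- The Table of Measures marks "VA Administrative Data", the source for treatment engagement, at 0 and 24 weeks only.
- The exploratory PCL model, described after Aim 2, is the only one whose time coding is spelled out: "indicators for each follow-up visit (at 8, 16, and 24 weeks), randomization group, and an interaction between the indicators for time and condition". Baseline is its reference.
- The Protocol (section 8h) excludes patients who "are already receiving psychotherapy or MH counseling". Chart review (section 11b) selects patients with no current or planned mental health treatment outside VA primary care.

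**The concern.** The outcome, the model terms and the named parameter do not fit together. A single yes/no per person has no time dimension, so time indicators, a person-level random effect and a condition-by-time interaction have nothing to act on. If there are repeated records, the SAP does not say what is recorded at each time, which time is the reference, or which combination of coefficients is tested.

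The analyst would have to choose the layout, reference and contrast when fitting the model. Depending on that choice, the named parameter cannot be estimated, has low power, or answers a question other than the stated one. This is a primary outcome, so the choice could decide the reported result.

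**Working it through.** **Inputs.** 114 randomized to CS PTSD Coach and 118 to TAU (Protocol, Continuing Review Form, item 1a); two-sided alpha .05 (SAP, Power Analysis). The documents give no specialty-visit rates, so every rate and count below is an assumption.

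**The plan's own binary power statement.** The SAP says the sample can detect a 20-point difference in percentages, without tying this to Aim 2. With 130 × 0.85 = 110.5, so 110 per arm, and the least favourable pair (40% vs 60%), the two-proportion formula gives Φ[(0.20 − 1.96 × 0.0674)/0.0661] = 84.8%. The statement therefore fits a direct comparison of one binary outcome per person.

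**Layout (a): one row per person, as the outcome is defined.** Every row is a week-24 row. The columns (intercept, condition, week 24, condition × week 24) take only the values (1,0,1,0) and (1,1,1,1). The rank is 2 for 4 columns, so the interaction is not identified.

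Nor is the random effect. With 26/130 vs 52/130 events, the maximised log-likelihood is −152.544 whether the random-effect SD is 0, 1, 2 or 4, while the fitted odds ratio moves from 2.67 to 3.19, 4.76 and 13.16.

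**Layout (b): rows at weeks 0 and 24, baseline as reference.** A post-randomization outcome has no defined week-0 value. Given the eligibility rules, an analogue would probably be at or near zero.

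Take an all-zero baseline and 57/114 vs 35/118 at week 24. The intercept runs to minus infinity and the week-0 rows contribute nothing, leaving

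114 ln(0.5) + 35 ln(35/118) + 83 ln(83/118) = −150.7586.

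With the random-effect SD near 0, this value is the same for every interaction tried from −3 to +3. Only condition plus interaction is determined, and only for a given SD: 0.864 at SD 0.02 and 1.038 at SD 1, with equal likelihood. If the true baseline rate were 1%, at least one arm would have no baseline event with probability 53%; at 2%, 18%.

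Now suppose a non-zero baseline visit variable existed, equal in both arms, with 50% vs 30% at week 24. The interaction estimate is logit(0.5) − logit(0.3) = 0.847. With independent records its variance is the sum over arms of [1/(p q) + 1/(b(1−b))]/n, where p is the week-24 rate, q = 1 − p and b is the baseline rate. At b = 5%:

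(4 + 21.05)/114 + (4.76 + 21.05)/118 = 0.4386, SE 0.662, power 25%.

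The direct comparison has power Φ[(0.20 − 1.96 × 0.0643)/0.0630] = 88%.

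| Baseline rate | Interaction, formula | Interaction, random-intercept simulation (300 runs) | Direct, formula |
|---|---|---|---|
| 2% | 14% | 7% (21% of runs had no usable fit, counted as non-rejections) | 88% |
| 5% | 25% | 24% | 88% |
| 10% | 37% | 37% | 88% |

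**Layout (c): cumulative indicators at several follow-up times, week 8 as assumed reference.** The interaction is

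[logit(p_CS,24) − logit(p_TAU,24)] − [logit(p_CS,8) − logit(p_TAU,8)],

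with per-arm variance [1/(p24 q24) + 1/(p8 q8) − 2/(q8 p24)]/n, where p24 and p8 are that arm's rates and q = 1 − p. These are marginal-formula figures, not rejection rates of the SAP's random-effect model.

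| Week 24, CS vs TAU | Week 8, CS vs TAU | Interaction rejects |
|---|---|---|
| 35% vs 35% | 15% vs 15% | 5% |
| 35% vs 35% | 15% vs 20% | 24% |
| 35% vs 35% | 10% vs 20% | 69% |
| 50% vs 30% | 10% vs 10% | 55% |
| 50% vs 30% | 24% vs 12% | 5% |

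With no difference at week 24 the test can reject 69% of the time. With a 20-point difference it can reject no more often than chance. At 50% vs 30% (week 24) and 30% vs 12% (week 8), the interaction is 0.847 − 1.145 = −0.298, an odds ratio of 0.74, which is the wrong direction.

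**The case against.** The best defence is that, with baseline as reference, randomization makes the baseline difference about zero, so the condition-by-week-24 interaction equals the 24-week effect. That works for the CAPS-5 or PCL-5. Here it needs a pre-randomization visit variable with a non-zero rate. Such a variable is possible: the Table of Measures does mark administrative data at week 0, and the exclusions concern current or planned treatment, not past visits. But the SAP does not define one.

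The power loss also depends on the assumed baseline rate. By the same formula, with within-person correlation 0, 0.2 and 0.4, interaction power is 51%, 60% and 72% at a 20% baseline, and 57%, 67% and 79% at 30%. So the 2% to 10% rows are the unfavourable end. The interaction still stays below 88% in all these cases.

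It is fair to say that each layout examined conflicts with some part of the SAP, and that the target itself is clear: an analyst guided by it could report the right contrast. That analyst would have to set aside the sentence that names the test. The grant protocol listed among the Protocol's attachments (section 16) is not available here and may define the time points. If so, the SAP needs to carry that definition.

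**Conclusion.** The concern holds, with high confidence, and should be fixed before the model is fitted. The named parameter is absent from the listed model and does not correspond to the stated outcome or target. In layout (a), and in layout (b) with no baseline events, it has no usable estimate; in layout (c) it is a different quantity from the 24-week effect. These are structural results and need no assumed rates.

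How much power is lost does depend on assumed rates: roughly 7% to 79% across the baseline-reference cases shown, against 88% for a direct comparison at 50% vs 30%. None of these figures estimates the trial's actual power. The sample size is not at fault, since the SAP's 20-point statement is consistent with a simple two-proportion comparison.

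**What to change.** Analyse one row per randomized participant. Fit a logistic regression of the week 1 to week 24 yes/no outcome on condition and site, and name the condition coefficient as the Aim 2 test. Site belongs in the model because randomization is run separately by site and Aim 1 already adjusts for it. Drop the random effect, the time indicators and the interaction. A risk difference with a 95% confidence interval is a useful optional addition.

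If the repeated-measures model is kept, define the outcome at each time and the reference time, list the interaction terms, and name condition plus interaction at 24 weeks as the test.

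The cost is a change of SAP wording, using the same administrative data. Enrollment is closed and the Continuing Review Form says the data are still being prepared for analysis. The change should therefore be a dated amendment that states whether outcome data by arm had been seen. It should also say how visits after withdrawal are counted, so that all randomized participants stay in the analysis.

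### The exploratory mediation rule reads any shift in the condition coefficient as a possible mechanism, with no interval for the indirect effect and no time order between coping and symptoms

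*SAP*

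**What the plan says.** The SAP's mediation plan is three sentences under Data Analysis, introduced by "Several approaches will be used to evaluate our Exploratory Aims". The candidates and models are: "To explore potential mediators (i.e., amount of app use, improvement in coping self-efficacy), we will fit 2 models for each potential mediator", then "One will include condition only and the second will include condition and the potential mediator". The reading rule is: "Change in the coefficient corresponding to condition after inclusion of the mediator may indicate a mechanism of action".

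Those sentences name no outcome, visit, lag, covariate or earlier symptom score, and no indirect-effect estimate or interval. Protocol section 2(a) lists coping self-efficacy among the measures of potential mediation and adds nothing on method.

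The SAP's Table of Measures gives the timing. Coping self-efficacy is taken at 0, 8, 16 and 24 weeks ("Coping Self-Efficacy Scale Coping Self-Efficacy X X X X"), as is the PCL-5 ("PTSD Checklist-Specific-5 (PCL-5) PTSD (self-report) X X X X"). CAPS-5 is marked only at 0 and 8 weeks, and Aim 1 concerns its change at 8 weeks.

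**The concern.** The rule has two gaps.

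**Sampling noise.** A coefficient almost always moves when a covariate is added. With no interval for the indirect effect, a reader cannot tell a real shift from chance.

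**Direction.** Feeling more able to cope may reduce PTSD symptoms, but fewer symptoms may also make people feel more able to cope. When both scores come from one visit, either direction makes the condition coefficient shrink. For CAPS-5 there is no way round this: the only post-baseline coping score that is not later than the outcome comes from the same week-8 assessment.

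What is at stake is the exploratory account of how the intervention works. Coping self-efficacy could be put forward as a mechanism on evidence that fits the opposite direction just as well.

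**Working it through.** The SAP states no figure for the mediation analysis, so there is none to reproduce. The checks ask how the rule behaves when the true answer is known.

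**Inputs from the SAP (Power Analysis):** d = 0.4, 110 evaluable per arm, two-sided 0.05. **Assumed, because the documents give no value:** all correlations and slopes between coping and PTSD scores, the effect of condition on coping, and score reliability.

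**1. Pure reverse causation, same visit.** Let condition shift the outcome Y by δ, and let coping M = cY + noise have no effect on Y. With within-arm correlation r:
- within-arm slope of Y on M = r²/c
- arm difference in M = cδ
- adjusted condition coefficient = δ − (r²/c)(cδ) = δ(1 − r²)

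| r (assumed) | shrinkage r² | δ = −0.40 becomes |
|---|---|---|
| 0.3 | 9% | −0.36 |
| 0.5 | 25% | −0.30 |
| 0.6 | 36% | −0.26 |
| 0.7 | 49% | −0.20 |

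The true mediated effect is zero in every row.

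**2. The same situation with baseline adjustment, by simulation.** Coping change follows symptom change with assumed slopes of 0.2, 0.4 and 0.6. The condition coefficient goes from −0.40 to −0.39, −0.35 and −0.30, a shrinkage of 4%, 13% and 25%. At 110 per arm the coping term is significant in 81%, 100% and 100% of trials, or 57%, 99% and 100% if PTSD-score reliability is 0.9. When coping truly drives symptoms, the coefficient also shrinks (−0.40 to −0.25 in one example). The rule responds alike to both directions.

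**3. No link at all between coping and outcome.** The shift in the coefficient is a × b, where a is the arm difference in coping and b is the fitted coping slope. With 220 participants and standardised scores, the standard error of b is about 1/√220 = 0.067. If condition raises coping by an assumed 0.5 SD, the shift has SD 0.5 × 0.067 = 0.034. A shift larger than 0.04 (a tenth of d = 0.4) then occurs when |Z| > 1.19, in about 23% of trials. With a = 0.3 SD the cut-off is |Z| > 1.98, about 5% by this approximation. Only an interval shows that such shifts are noise.

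**4. What time order can and cannot add.** Take coping change to week 8 as mediator and week-16 PCL-5 as outcome.
- *Lag alone, reverse causation:* the coefficient still shrinks by 4% to 25%, and coping is significant in 41% to 100% of trials. Lagging without week-8 PCL-5 does not help.
- *Lag plus baseline and week-8 PCL-5, error-free scores, reverse causation:* coping is significant in 4.6% to 6.5% of trials, close to the nominal 5%.
- *The same with PTSD-score reliability 0.9:* 6% to 12%. The false coping coefficient depends on the set-up. One simulation gave −0.02 to −0.07 at reliability 0.9; another gave −0.08 at reliability 0.9, growing to −0.21 at 0.7.
- *Coping as the only mechanism, complete by week 8:* the same-visit coefficient goes correctly from −0.36 to 0.00. The lagged model gives coping a coefficient of 0.00, although the total effect at week 16 is −0.25. It misses the mechanism altogether.

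**The case against.** **The plan is modest about this analysis.** The aim is exploratory and the SAP says only that a shift may indicate a mechanism. A reader might infer that the trial will report coping as an established mechanism; the text does not go that far, and no primary conclusion, sample size or safety decision depends on it. This stands and limits the weight of the point. Cautious wording still does not supply an interval or a direction.

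**The SAP does not prescribe a same-visit CAPS-5 mediation model.** A reader might infer one from Aim 1. The mediation sentences name no outcome, and the same part of the SAP models PCL scores at all visits. This also stands: the fault is an omission that permits the weak analysis. The statement about CAPS-5 is conditional on its being the mediation outcome.

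**A lagged model is not simply better.** It is tempting to say that the time-ordered scores already collected should replace the planned comparison. Treatment is four sessions and week 8 is the post-treatment visit, so much of any mechanism may be over by then, and adjusting for week-8 PCL-5 removes it. The lagged model also exchanges a blinded interview for self-report, and measurement error in the PCL-5 can create a false signal. Step 4 bears this out, so the lagged model can only sit beside the main analysis.

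**The sizes rest on assumptions.** They do. The two sets of calculations overlap only at 25%, and low correlations give small shrinkage. The direction of the distortion does not depend on the values chosen.

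**Conclusion.** The point holds as a low-cost improvement to an exploratory analysis. As written, the rule treats an untested shift in a coefficient as possible evidence of mechanism, without an interval and without time order. If CAPS-5 is the outcome, the shift could equally reflect symptom relief raising coping. Under that explanation alone the apparent mediated share is about 9%, 25% or 49% at assumed within-arm correlations of 0.3, 0.5 or 0.7, and 4% to 25% in the baseline-adjusted simulation. The documents contain nothing to narrow that range.

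They do not support the claims that the SAP commits to a same-visit analysis, that the trial will announce a mechanism, or that a lagged model should be the only analysis. Aims 1 and 2 are untouched.

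**What to change.** For the coping self-efficacy mediator, amend the SAP to:

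1. Name the outcome and the visits at which mediator and outcome are taken.
2. Report the indirect effect with a bootstrap 95% CI, adjusted for site and for baseline coping and symptom scores, in place of the bare change in coefficient.
3. Describe any same-visit result as an association that cannot establish direction. The interval deals with sampling noise only; under reverse causation it can still exclude zero.
4. Add, as a sensitivity analysis and not a replacement, week-8 coping against 16- and 24-week PCL-5, adjusted for baseline and week-8 PCL-5.

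**Cost.** A little more analysis work and no new data, since both scales are scheduled at all four visits. The continuing review form says data were still being prepared for analysis, with no interim findings to report. If that is still so, the change can be dated before the mediation models are run.

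**Limits to state with it.** The lagged analysis misses mediation completed by week 8, uses self-report PCL-5 and not CAPS-5, and can give a false signal from measurement error in PCL-5. Neither a null nor a positive lagged result settles the matter. Unmeasured causes of both coping and symptoms remain a threat to either analysis.

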At the baseline appointment (which will be held in person or by phone), research staff will obtain oral informed consent and HIPAA authorization. Next self-report measures will be administered to assess eligibility. Participants will be randomized to 1) PC-MHI TAU or 2) CS PTSD Coach. Within a week of baseline (and before session 1) participants will complete the CAPS-5 by phone with an independent assessor. A post-treatment assessment (8 weeks) and two follow-up assessments (16 weeks and 24 weeks) will be conducted following baseline. These will be completed via survey link (from a no-reply email from REDCap), or by phone (based on participant preference), with the exception of the CAPS-5, which will be by phone.

There are two study conditions: 1) Clinician-Supported PTSD Coach (CS PTSD Coach) consists of four 20-30 minute sessions focused on assigning specific PTSD Coach activities. Existing PC-MHI providers will deliver CS PTSD Coach following a treatment manual. Participants can use their own smart device or borrow a study-owned iPod Touch. During the baseline session after randomization, research staff will assist in downloading the research version of the PTSD Coach app on the device. This version of PTSD Coach allows for collection of de-identified app usage data, including how much and often the app was used, date and time of use, duration of use, assessment item

**Title :** An RCT of a Primary Care-Based PTSD Intervention: Clinician-Supported PTSD Coach  
**Approval Period:** Draft

responses, and which components of the app were used. Participants are assigned a unique, randomly-generated string of alpha-only characters (over 308 million possible permutations) that unlocks the app and allows for a de-identified link between the participant's mobile device and the HIPAA-compliant research server where the app data is stored. The research version of PTSD Coach does not allow for the collection of any personally-identifying information and does not contain any open text fields that would enable participants to enter personally-identifying information. Within one week, participants will complete session 1, which may be face-to-face or by phone (as will sessions 2-4), depending on patient preference and if conditions related to COVID-19 have been resolved. At the 4th session, participants scoring  $\geq 33$  on the PCL-5 (probable PTSD), will be recommended for specialty MH treatment.

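### Continued app use and receipt of MH treatment arise after randomisation, so the exploratory interactions with them should not be read as moderation of the CS PTSD Coach effect

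*SAP*

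**What the plan says.** The sentence at issue is in the SAP, Data Analysis and Statistical Considerations, after the mixed model for PCL scores at all time points: "We will also explore if trajectories are moderated by continued PTSD Coach use and receipt of MH treatment". The paragraph is exploratory and opens "Several approaches will be used to evaluate our Exploratory Aims".

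The same paragraph says how moderators are handled: "To examine possible moderators (e.g., baseline PTSD severity), interaction terms between possible moderators and condition will be assessed". The example given is a baseline variable. The reading rule follows: "Significant interaction terms will suggest that the effect of intervention varies by" the level of the moderator. App use also appears there in a second role: "To explore potential mediators (i.e., amount of app use, improvement in coping self-efficacy), we will fit 2 models for each potential mediator".

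For Aim 2, the SAP evaluates the effect of condition on the "rate of attendance to at least 2 specialty MH visits post randomization (week 1 to week 24").

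Protocol section 2 (Study Procedures) places the app after allocation, within the description of the CS arm: "During the baseline session after randomization, research staff will assist in downloading the research version of the PTSD Coach app on the device". It also says that a CS participant with a score of 33 or more at the fourth session "on the PCL-5 (probable PTSD), will be recommended for specialty MH treatment". The TAU description has neither an app component nor a PCL-5 referral threshold.

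**The concern.** A moderator analysis compares the arms within levels of a third variable. That comparison keeps the protection of randomisation only if allocation cannot influence the variable. Here it can. The trial hopes to change specialty attendance, and in the CS arm an earlier score on the outcome instrument feeds into who is advised to seek care. Receivers in the two arms may then be differently selected people, and the arm contrast among them mixes the treatment effect with that selection.

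At stake is a question the trial is built around: a brief primary-care intervention followed, where needed, by specialty care. A selection artefact could be reported as CS PTSD Coach working less well in people who went on to care, or as specialty care going with worse outcomes. The SAP's reading rule gives no protection against either conclusion, and it names no lagged, landmark, time-varying or causal method for these two variables.

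**Working it through.** The plan states no power, error rate or sample size for this analysis, so there is no figure to reproduce. The check has three parts.

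**1. Timing and role of each variable**

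| | Receipt of MH treatment | Continued app use |
|---|---|---|
| When it arises | After entry: patients already in psychotherapy or MH counselling are excluded (Protocol 8h) | After allocation: the research app is installed after randomisation (Protocol 2) |
| Can condition affect it? | Expected: specialty attendance is the Aim 2 outcome. The pilot reported more specialty PTSD care use than with self-managed PTSD Coach (Protocol 3) | Yes: the app is part of the CS condition |
| Other role in the SAP | Closely related to the Aim 2 outcome | Mediator |
| Recorded in both arms? | Yes, administrative data | Described only for CS |

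**2. App use: estimability**

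Write the model as Y = b0 + b1·A + b2·U + b3·A·U, with A = 1 for CS and U for logged use. If U is unrecorded in TAU, those rows drop out and A is constant. If U is set to 0 in TAU, then A·U = U for everyone, so b2 and b3 cannot be separated. The condition-by-use interaction is not estimable either way.

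**3. Receipt of care: size of the selection effect**

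Let the true effect be δ for everyone, and let M(1) and M(0) be receipt under CS and TAU. The contrast among receivers is

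δ + { E[Y(0) | M(1)=1] − E[Y(0) | M(0)=1] }.

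The bracket is zero only if the two sets of receivers have the same prognosis.

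*Large-sample illustration.* All inputs are assumed except the cut-off of 33. Baseline PCL-5 is N(50, 11) truncated at 33. The 8-week score is baseline − 6 + δ + N(0, 12), with δ = −5 in CS. The 24-week score regresses 0.75 on the 8-week score around each arm's own mean, with residual SD 9. Care has no effect. The 8-week score stands in for the fourth-session score. The outcome is change from baseline to 24 weeks, so the true arm means are −6 − 5 = −11 (CS) and −6 (TAU).

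Take uptake of 50% at or above 33 and 15% below, with TAU uptake 30% at random:
- CS: receivers −9.2, non-receivers −12.2. TAU: −6.0 in both groups.
- Apparent CS effect: −9.2 + 6.0 = −3.2 in receivers; −12.2 + 6.0 = −6.2 in non-receivers.

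Take the same 50%/15% rule in both arms:
- TAU: receivers −4.6, non-receivers −7.1.
- Apparent CS effect: −9.2 + 4.6 = −4.6; −12.2 + 7.1 = −5.1. Repeat runs gave −4.5 to −4.6 for receivers.

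| Uptake at or above/below 33 | TAU uptake | Receivers | Non-receivers | False interaction | Receivers minus non-receivers within CS |
|---|---|---|---|---|---|
| 50%/15% | random | −3.2 | −6.2 | 3.0 | about +3 |
| 50%/15% | same rule | −4.6 | −5.1 | 0.5 to 0.6 | about +3 |
| 40%/20% | random | −3.8 | −5.6 | 1.8 | +1.8 |
| 40%/20% | same rule | −4.7 to −4.8 | −5.1 | 0.4 | +1.8 |
| unrelated to PCL-5 | random | −5.0 | −5.0 | 0 | 0 |

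*Finite-sample check.* This used 110 per arm (the SAP's figure after 15% loss), 2,000 trials per setting and a separate fourth-session score as trigger. There was no true moderation. The outcome was mean PCL-5 at 8, 16 and 24 weeks minus baseline, and the interaction was tested by least squares at two-sided 0.05. Assumed: PCL-5 mean 48, effect −5, TAU uptake 20% at random, CS uptake from 30%/15% to 60%/10%; in the settings that vary persistent individual change, between-person SD 11 and residual SD 6.

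| SD of persistent individual change | False-positive rate | Interaction bias (points) |
|---|---|---|
| 0 (including other correlation structures) | 4.8–7.2% | +0.3 to +0.9 |
| 6 | 7–15% | +1.1 to +2.7 |
| 10 | 9–30% | +2.1 to +5.2 |
| 14 | 10–45% | +3.8 to +8.6 |

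With uptake unrelated to the score the rate was 4.1–5.5%. With the same 40%/10% rule in both arms it was 4.8–6.1%, but the within-CS comparison was still off by +0.5 to +6.2 points.

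**The case against.** The strongest defence has four parts.

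- **Status.** This is one exploratory sentence, and its verb is to explore. That stands: the Aim 1 and Aim 2 tests are untouched.
- **Model.** The sentence does not write out a product term with condition. A time-by-use analysis within the CS arm is an open reading. That stands as a fair reading, but the only rule the SAP gives for moderators is an interaction with condition, read as variation in the intervention effect. Under the narrower reading, the within-arm comparison by receipt of care is still subject to selection.
- **Definition.** Receipt of MH treatment is not the same variable as at least two specialty visits. This also stands. It adds to the problem, since variable, window and model are all left undefined.
- **Size.** The documents describe no TAU referral threshold, but they do not say that TAU uptake ignores severity, and TAU providers also assess and refer. With the same uptake rule in both arms, the false interaction falls from 3.0 to 0.5–0.6 points. This stands, and it is why both cases are shown.

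A reader might infer that receipt is a direct consequence of the PCL-5 score being modelled. The documents do not support that. The trigger is the fourth-session score, while the model uses 0, 8, 16 and 24 weeks. It leads to a recommendation, not to receipt. The link is an earlier score on the same instrument that may partly drive uptake.

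**Conclusion.** The point holds as a matter of interpretation. Both variables arise after randomisation and may be affected by condition. A condition-by-receipt interaction could therefore be biased and should not be read as effect modification. A condition-by-app-use interaction cannot be estimated from the usage data described.

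The size is uncertain. For a uniform −5 effect, no effect of care and 50%/15% uptake, the receiver/non-receiver split is about −3.2/−6.2 if TAU uptake is random and about −4.6/−5.1 if TAU uptake follows the same rule. Receivers within CS look about 3 points worse in both cases. These figures depend on uptake rates, PCL-5 variances and the TAU pattern, none of which the documents give.

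A reader might go further and conclude that any moderation found would necessarily be spurious, or that the analysis would show specialty care as harmful. Neither follows. In some settings the bias is negligible and the false-positive rate stays near 5%; in the most adverse setting tried it reached about 45%. This should be corrected before the exploratory results are read, but it does not threaten the main conclusions.

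**What to change.** Limit moderator tests to baseline variables, such as the baseline PTSD severity already listed. Replace the sentence with two descriptive analyses:

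- **App use:** within the CS arm only, describe later PCL-5 by continued app use. State the window in which use is counted and take PCL-5 after it.
- **MH treatment:** report the association of later PCL-5 with treatment received by a fixed landmark, using the visit dates already extracted (Protocol 11b). Two options are treatment by week 8, adjusted for baseline PCL-5, with PCL-5 at weeks 16 and 24 as outcome; or treatment between weeks 8 and 16, adjusted for week-8 PCL-5, with week 24 as outcome. The adjustment score must be the last scheduled one before the window, defined identically for receivers and non-receivers. A score taken before the first visit does not exist for people with no visit. Define which contacts count as MH treatment, and whether PC-MHI visits are included.

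Label both as exploratory associations, not moderation, since confounding by severity may remain after adjustment.

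The cost is SAP wording and no new data. The moderation claim is given up, and visits after the landmark are not used. Protocol continuing review item 3a reports data still being prepared with no interim findings, so at that stage the change could precede results.
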